9.6.2.2. Secondary Efficacy Endpoints Analyses

According to the hierarchical method to control inflation in type I error rate for multiple endpoints, any statistically significant dose that will be observed in the primary analysis will continue to be tested for the secondary endpoints at an alpha level of 5%, according to the secondary endpoints order.

The secondary efficacy endpoints: change from baseline in HD-CAB total score and change from baseline in UHDRS- TFC, will be analyzed in the same way as the primary efficacy endpoint except that the efficacy endpoint evaluation at baseline will be included in the model instead of baseline UHDRS-TMS.

The CIBIC-Plus will be analyzed in the same way as the primary efficacy endpoint except that the baseline CIBIS (Clinician's Interview-Based Impression of Severity) will be included in the model as the efficacy measure at baseline.

The percent change from baseline to Month 12/Early Termination in caudate volume will be analyzed using an Analysis Of Covariance (ANCOVA) model (SAS® MIXED procedure). The model will include the following fixed effects: treatment, center, and caudate volume at baseline.

The estimated means at the Month 12 visit will be compared between the active treatment arms and the placebo arm. Early terminated patient observation will have their Last Observation Carried Forward (LOCF).

9.6.2.3. Exploratory Efficacy Endpoints Analyses

The exploratory efficacy endpoints will be analyzed in the same way as the primary efficacy endpoint except that the efficacy endpoint evaluation at baseline will be included in the model instead of baseline UHDRS-TMS.

The change from baseline to Month 12/Early Termination of continuous efficacy endpoints that are measured at baseline and at month 12 only, will be analyzed using an ANCOVA model (SAS® MIXED procedure). The model will include the following fixed effects: treatment, center, and the efficacy measure at baseline. The estimated means at the Month 12 visit will be compared between the active treatment arms and the placebo arm. Early terminated patient observation will have their Last Observation Carried Forward (LOCF).

9.6.2.4. Sensitivity Analysis

No sensitivity analyses are planned for this study.

9.6.2.5. Pooling of Small Centers

Centers with low number of patients will be pooled according to geographical region.

Details will be provided in the Statistical Analyses Plan (SAP).

The pooled center variable will be used in all statistical models that include center as covariate.

9.7. Multiple Comparisons and Multiplicity

The Hochberg's Step-Up method for multiple comparisons between treatment arms in combination with the hierarchical method between the primary efficacy endpoint and the secondary efficacy endpoints, will be used to maintain the experiment wise type I error of 5% level. First, the Hochberg method will be applied for the comparisons of the 2 active doses to placebo in the primary endpoint analysis. Then, using the hierarchical method, any statistically significant dose will continue to be tested for the secondary endpoints at an alpha level of 5% and according to the order of the secondary endpoints.

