9. STATISTICS

9.1. Study Design and Randomization

This is a double-blind, randomized, placebo-controlled, parallel-group study to evaluate the efficacy and safety of laquinimod (0.5 mg and 1.0 mg qd) treatment in patients with HD. Prior to 10 January 2016, eligible patients were randomly assigned to receive treatment with laquinimod at a dosage of 0.5 mg, 1.0 mg, or 1.5 mg/day or a matching placebo in a 1:1:1:1 ratio. Randomization will be as described in Section 3.3.

As of 10 January 2016, following a decision to discontinue treatment of the laquinimod 1.5 mg dose arm, future eligible patients will be randomized in a 1:1:1 ratio to receive laquinimod 0.5 mg/day or 1.0 mg/day or matching placebo for 52 weeks.

No change was performed to the original randomization list except that the patient numbers assigned to laquinimod 1.5 mg/day were removed from the list by the IRT vendor. Patients and investigators will remain blinded to treatment assignment during the study.

All patients who discontinued the 1.5 mg/day dose have been unblinded. No attempts will be made to re-randomize patients whose 1.5 mg treatment was stopped to a lower dose of laquinimod. The remaining ongoing patients retained their originally randomized treatment assignments.

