9.2. Sample Size and Power Considerations

The study aims to detect potential beneficial effects in deteriorating clinical signs and symptoms. Based on previous studies in patients with HD, the UHDRS-TMS has been shown to be one of the more sensitive clinical measures to detect decline in symptoms of HD. It is estimated that approximately 100 patients per arm will enable a power of 80% to detect a beneficial effect compared to placebo, of 2.5 points or more in the change from baseline in UHDRS-TMS of an active laquinimod arm, assuming SD of 6.2 and type I error of 5%.

As the intention is to investigate laquinimod as a treatment with the potential to slow disease progression and prohibit neuronal death in the CNS, the study should also be sized to be able to detect changes in brain atrophy rate after treatment with laquinimod. One of the most sensitive measures to detect brain atrophy over time in patients with HD is change in the caudate volume.

It is estimated that approximately 100 patients per arm will enable a power of 80% to detect a beneficial effect of 0.95 (30% of the estimated decline in placebo) or more in the percent change from baseline in caudate brain atrophy of an active laquinimod arm compared to placebo, assuming SD of 2.36 and type I error of 5%.

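### Testing each passing dose on the secondaries at a full 5% breaks the claimed 5% experiment-wise error, which can reach about 9–10%

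*Protocol*

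**What the plan says.** Section 9.7 combines Hochberg's step-up method between arms with a hierarchical order between endpoints and says the combination "will be used to maintain the experiment wise type I error of 5% level". It then fixes the mechanics. First, "the Hochberg method will be applied for the comparisons of the 2 active doses to placebo in the primary endpoint analysis". After that, "any statistically significant dose will continue to be tested for the secondary endpoints at an alpha level of 5"%, following the order of the secondary endpoints: caudate volume, HD-CAB total score, CIBIC-Plus, UHDRS-TFC.

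Section 9.6.2.2 repeats the rule: a dose that succeeds on the primary "will continue to be tested for the secondary endpoints at an alpha level of 5%, according to the secondary endpoints order". The synopsis repeats both the claim and the rule. For caudate volume, Section 9.6.2.2 gives a separate ANCOVA in which "The estimated means at the Month 12 visit will be compared between the active treatment arms and the placebo arm". It mentions no adjustment between the two doses.

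**The concern.** A fixed order protects across endpoints within one dose. It gives no protection across two doses that each run their own order. If both doses pass the primary, two caudate tests are made side by side, each at 5%. If only one dose truly works on TMS, its secondary chain runs at 5%. Meanwhile the other dose's true primary null is also exposed at 5%, because Hochberg allows rejection at 5% once the other p-value is below 5%. The two chances of error add up, and no step in the plan limits the total.

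Caudate volume carries the disease-modification argument, and Section 9.2 says the study should also be sized for it. A positive caudate, HD-CAB, CIBIC-Plus or TFC result would be presented under a 5% error rate that the procedure does not deliver.

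**Working it through.** **Inputs from the protocol.** Two doses against one placebo arm, Hochberg at 5% on the primary, then 5% per passing dose (Sections 9.7 and 9.6.2.2). Equal allocation of the three analysed arms (Section 9.1) with about 100 patients each (Section 9.2). TMS effect 2.5, SD 6.2; caudate effect 0.95, SD 2.36 (Section 9.2).

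**Assumptions.** Two-sided tests, normal test statistics, and a correlation between TMS and caudate of 0, 0.3 or 0.6, which the protocol does not give. Equal arms sharing one placebo give a correlation of 0.5 between the two dose–placebo contrasts.

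**1. The plan's own sample size.** For TMS, 2.5 / (6.2 × √(2/100)) = 2.85, giving power of 81.4% at 100 per arm (97 per arm needed for 80%). For caudate, 0.95 / (2.36 × √(2/100)) = 2.85, giving power of 81.2% (again 97 per arm). Both agree with the stated 100 per arm and 80%, which supports the two-sided reading.

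**2. No dose works on TMS.** Hochberg rejects both doses if both p ≤ 0.05, and otherwise a single dose with p ≤ 0.025. Simulated error is 4.8%. The primary family is controlled.

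**3. Both doses clearly effective on TMS, caudate null for both.** Both doses pass, so the error is

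1 − P(|Z₁| ≤ 1.96 and |Z₂| ≤ 1.96), correlation 0.5 = **9.07%**.

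For comparison, independent contrasts would give 1 − 0.95² = 9.75%, and the upper bound is 5% + 5% = 10%. Counting only false claims of benefit, the figure is 4.5% against a nominal 2.5%.

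**4. One dose clearly effective on TMS, the other null, caudate null.** The effective dose passes, so the other dose's primary is judged at 5% and the effective dose's caudate test at 5%. If these are independent, 1 − 0.95² = 9.75%. Simulation (1,000,000 trials) gives about **9.5–9.7%** over endpoint correlations of 0 to 0.6.

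**5. At the planned 2.5-point TMS effect, caudate null** (1,000,000 simulated trials per cell):

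| Endpoint correlation | Both doses active on TMS | One dose active on TMS |
|---|---|---|
| 0 | 7.2% | 7.8% |
| 0.3 | 6.8% | 7.5% |
| 0.6 | 5.7% | 7.0% |

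**6. Candidate repairs, largest error over the same configurations:**

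| Procedure | Maximum error |
|---|---|
| Protocol rule | 9.7% |
| Hochberg repeated at each secondary, among passing doses | 9.8% |
| Hochberg on the primary, secondaries at 2.5% per dose | 7.4% |
| Secondaries opened only if both doses pass, then Hochberg | 5.0% |
| Two dose-specific chains at 2.5% throughout | 4.9% |

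Repeating Hochberg on the secondaries, or only lowering their level, is therefore not enough. The primary and secondary steps have to be treated together.

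**The case against.** The 9–10% figures are limits. They need a TMS effect so large that passing the primary is nearly certain. At the planned effect the excess over 5% is roughly 0.7 to 2.8 percentage points, and when neither dose works on TMS there is none. This is fair, and the planned-effect figures belong beside the maximum. But a claim of experiment-wise control has to hold whatever the true effects are, and the protocol makes it without qualification.

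The trial is Phase II and a first proof of concept in this disease. The primary comparison is valid, and each dose's own chain is held at 5%. That bears on how grave the error is, not on whether the statement is true.

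One could read the wording that the secondaries are analysed in the same way as the primary as carrying Hochberg forward. That wording covers HD-CAB, TFC and CIBIC-Plus, but not caudate, which comes first in the order. Even if it covered all four, the error would still reach about 9.7% when only one dose works on TMS.

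The objection that stands is cost. Only the restricted claim is purely a change of wording; the two procedural repairs give up power or formal secondary claims.

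**Conclusion.** The protocol is wrong as written. It states a 5% experiment-wise error and, in the same section, fixes a rule that does not provide it, so this is not a detail left to the statistical analysis plan. The error rate is about 4.8% when neither dose affects TMS, about 5.7–7.8% at the planned effect, and at most 9.1% (both doses clearly effective) to about 9.7% (one dose clearly effective), with an upper bound of 10%. Inflation arises only when at least one dose truly works on TMS and a secondary that is then tested is null. The figures rest on two-sided tests, equal arms of about 100, normal statistics, and endpoint correlations of 0 to 0.6. Results on the primary endpoint are unaffected.

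**What to change.** Amend Sections 9.7 and 9.6.2.2 and the matching synopsis text before the continuing arms are unblinded. There are three sound choices:

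- **Restrict the claim.** State that 5% control covers the two primary comparisons only, and that the secondaries are controlled at 5% within each dose, with an overall error of up to about 10%. This costs nothing but wording.
- **Gate on both doses.** Keep Hochberg on the primary. Open caudate only if both doses pass, test it with Hochberg across doses, and open each later secondary only if both doses pass the one before. Report the secondaries of a single passing dose as nominal. Primary power is unchanged, but there is no formal secondary test when one dose succeeds. Section 1.5 describes results in other diseases where 0.5 mg did better than 1.0 mg, so that outcome is realistic.
- **Two dose-specific chains at 2.5% each**, primary then secondaries in order, passing the 2.5% to the other dose only when a chain is rejected in full. This keeps formal secondary tests for a single dose. When both doses work at the planned effect, primary power per dose falls from about 79% under Hochberg to about 73%. Restoring 80% at 2.5% would need about 117 per arm.

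Choosing between the last two is a design preference. If neither cost is acceptable, the first choice is the minimum.

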9.8. Safety Variables and Analysis

9.8.1. Safety Variables

Safety variables and endpoints will include the following:

- Adverse events reports throughout the study
- ECG findings throughout the study
- Clinical safety laboratory tests throughout the study
- Vital signs measurements throughout the study
- Physical examination findings throughout the study
- Changes from baseline suicidality (C-SSRS) scores throughout the study

Tolerability variables:

- Proportion of subjects (%) who prematurely discontinued from the study, reason of discontinuation and the time to ET
- Proportion of subjects (%) who prematurely discontinued from the study due to AEs and the time to ET

9.8.2. Safety Analysis

All adverse events will be coded using the Medical Dictionary for Regulatory Activities (MedDRA). Each patient will be counted only once in each preferred term or system organ class (SOC) category for the analyses of safety. Summaries will be presented for all adverse events (overall and by severity), adverse events determined by the investigator to be related to study treatment (ie, reasonable possibility; see Section 7.1.4) (defined as related or with missing relationship) (overall and by severity), serious adverse events, and adverse events causing withdrawal from the study. Summaries will be presented by treatment group and for all patients. Patient listings of serious adverse events and adverse events leading to withdrawal will be presented.

Changes in laboratory and vital signs measurement data will be summarized descriptively. All values will be compared with prespecified boundaries to identify potentially clinically significant changes or values, and such values will be listed.

The use of concomitant medications will be summarized by therapeutic class using descriptive statistics. Concomitant medications will include all medications taken while the patient is treated with study drug.

For continuous variables, descriptive statistics (n, mean, standard deviation, standard error, median, minimum, and maximum) will be provided for actual values and changes from baseline to each time point. For categorical variables, patient counts and percentages will be provided. Descriptive summaries of serious adverse events, patient withdrawals due to adverse events, and potentially clinically significant abnormal values (clinical laboratory or vital signs) based on predefined criteria will also be provided.

If any patient dies during the study, a listing of deaths will be provided and all relevant information will be discussed in the patient narrative included in the clinical study report.

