3. STUDY DESIGN

3.1. General Design and Study Schema

This is a multicenter, randomized, double-blind, placebo-controlled, parallel-group study to evaluate the efficacy and safety of laquinimod treatment at dosages of 0.5, 1.0, and 1.5 mg/day in adults with Huntington's Disease.

The study will consist of a screening period (2 weeks up to 5 weeks), followed by a 52-week double-blind treatment period and a follow-up visit (one month after end of treatment). Prior to 10 January 2016, a total of 400 patients were planned to be equally randomized in a 1:1:1:1 ratio (100 patients within each treatment arm) to receive laquinimod 0.5, 1.0, 1.5 mg/day, or matching placebo for 52 weeks. A total of 123 patients were randomized prior to 10 January 2016.

As of 10 January 2016, following the decision to discontinue treatment of the laquinimod 1.5 mg dose arm, additional eligible patients who are enrolled will be randomized in a 1:1:1 ratio to receive laquinimod 0.5 mg/day, 1.0 mg/day, or matching placebo for 52 weeks. Approximately 300 patients (100 patients within each study arm), plus the 30 patients who were already randomized to the laquinimod 1.5 mg treatment arm, are planned to be enrolled in the study.

After signing the informed consent, including consent to provide a blood sample for genetic analyses including CAG repeat length analysis, patients will be screened for a period of 2 weeks up to 5 weeks in order to determine whether they are eligible to participate in the study. Patients with a legal guardian should be consented according to local requirements.

The procedures and assessments performed during each of the study visits are detailed in Section 3.11.

During the visits, vital sign measurements, physical examinations and ECG should preferably be performed prior to the blood draw for clinical laboratory tests and pharmacokinetic sampling. Further, the efficacy assessments (TMS, HD-CAB, CIBIC-plus and TFC) should be done prior to the exploratory assessments.

Patients who complete all scheduled visits will have final procedures and assessments performed at the final visit (Visit 8, Month 12). Patients who withdraw from the study before completing the 52-week evaluation period will have Visit 8 procedures and assessments performed at their last visit.

An independent DSMB will oversee the study. The DSMB will review unblinded accumulating safety data on a regular basis to ensure the continuing safety of the study patients and study conduct issues.

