In blinded studies, for adverse events that are defined as: Suspected, Unexpected, Serious, Adverse Reaction (SUSAR) (ie, reasonable possibility; see Section 7.1.4), Global Patient Safety and Pharmacovigilance may independently request that the treatment code be revealed (on a case-by-case basis) to comply with regulatory requirements. If this occurs, the investigator will remain blinded to treatment.

As of 10 January 2016, treatment with laquinimod was discontinued for all patients in the 1.5 mg dose group; all these discontinued patients have been unblinded. No attempts will be made to re-randomize patients whose 1.5 mg treatment was stopped to a lower dose of laquinimod.

However, the blinding was maintained for the patients in the remaining ongoing 3 treatment arms (0.5 mg/day, 1.0 mg/day, and placebo).

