3.10. Time Schedule

The study started in Q4 2014 (first patient randomized) and is expected to be completed in Q1 2018 (last patient last visit).

As of 10 January 2016, treatment with laquinimod was discontinued for all patients in the 1.5 mg/day dose arm.

Approximately 300 patients (100 patients within each study arm), plus the 30 patients who were already randomized to the laquinimod 1.5 mg dose arm, from ~51 investigational centers in North America, Europe and Russia are planned to be enrolled in the study.

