9.3. Analysis Sets/Populations

Due to the decision from 10 January 2016 to discontinue treatment of the laquinimod 1.5 mg dose arm, and the low number of enrolled patients compared to the target at this time, data from the laquinimod 1.5 mg dose arm will be presented descriptively only and will not be included in any inferential analyses for efficacy or safety.

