9.3.2. Safety Population

The safety population will include all randomized patients who receive at least 1 dose of study drug. In this population, treatment will be assigned based upon the treatment patients actually receive, regardless of the treatment to which they were randomized.

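### Crude adverse event percentages were kept when the 1.5 mg arm was stopped early, so for events spread over time that arm's figures tend to understate risk and are not comparable with the 52-week arms

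*Protocol*

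**What the plan says.** Section 9.8.2 of the protocol defines the AE summary directly, without deferring to the SAP. The counting rule is "Each patient will be counted only once in each preferred term or system organ class (SOC) category for the analyses of safety", the statistic is "For categorical variables, patient counts and percentages will be provided", and the layout is "Summaries will be presented by treatment group and for all patients". The denominator comes from Section 9.3.2: "The safety population will include all randomized patients who receive at least 1 dose of study drug". The 1.5 mg arm therefore has its own column. Under Section 9.3 its data "will be presented descriptively only and will not be included in any inferential analyses for efficacy or safety".

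On exposure, Section 3.8 says: "As of 10 January 2016, treatment with laquinimod was discontinued for all patients in the 1.5 mg dose group". Section 3.10 places the first randomization in Q4 2014. Section 3.1 says "A total of 123 patients were randomized prior to 10 January 2016", puts the 1.5 mg arm at 30 patients, and plans about 100 patients in each continuing arm for 52 weeks.

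Two places bear on which events count after the stop. Section 7.1.2 ends AE recording one month after the last dose. Section 3.11.3.1.5 asks the stopped 1.5 mg patients to keep attending scheduled visits for safety.

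The protocol names no person-time or time-to-event AE summary. The one time-based safety or tolerability item is time to early termination (Section 9.8.1). The change table for Amendment 04 (Section 16.1) lists revisions to Sections 9.1, 9.3, 9.7, 9.9.1 and 9.9.2, and none to 9.8.2.

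**The concern.** The share of patients with an event compares arms fairly only if they were observed for similar times. Here one arm was cut off on a single calendar date and the others run to a planned 52 weeks. An event that accrues steadily has less time to appear at 1.5 mg, so its percentage there will tend to be lower even if the rate on drug is the same or higher.

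This matters because Section 2.1 gives the study's purpose as the efficacy and safety of 0.5, 1.0 and 1.5 mg. The arm was closed over a cardiovascular imbalance at high doses in the multiple sclerosis trials, where Section 1.4.1.2.7 reports no specific time-to-event pattern. Events of that kind are the ones a crude percentage handles worst under unequal exposure. The same section describes the multiple sclerosis evidence in patient-years.

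**Working it through.** **Arm size.** The protocol gives no AE rate or exposure for the 1.5 mg arm; the figure that can be reproduced is its size. Under 1:1:1:1 allocation, 123 / 4 = 30.75, which agrees with the stated 30.

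**Inputs from the protocol.** Stop date 10 January 2016; first randomization between 1 October and 31 December 2014, giving 466 or 375 days of accrual; planned treatment 52 weeks (364 days); AE recording to last dose plus 1 month.

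**Assumptions.** Accrual is either uniform or rising linearly. Full exposure is assumed in the continuing arms. The AE risks are illustrative.

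**Exposure.** Each patient's exposure is the smaller of the time from randomization to the stop and 364 days, in 52-week years. Let L be the accrual days and c = 364/L (0.781 or 0.971).

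- Uniform: mean = (182 + L − 364) / L. For L = 466, 284/466 = 0.61. For L = 375, 193/375 = 0.51.
- Rising: mean = [1 − (1 − c)³] / (3c). For L = 466, 0.42. For L = 375, 0.34.

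The share reaching 52 weeks ranges from about 0% to 22%. Over 30 patients, total exposure is about 10 to 18 patient-years.

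**Constant-rate event, same rate in every arm.** Take a 20% risk over 12 + 1 months: λ = −ln(0.8) / (13/12) = 0.206 per year. The crude percentage at 1.5 mg is the mean of 1 − exp[−λ(e + 1/12)] over the exposures e.

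| Accrual | Mean exposure (years) | Crude % at 1.5 mg | Rate ratio needed to show 20% |
|---|---|---|---|
| Uniform, L = 466 | 0.61 | 13.1 | 1.61 |
| Uniform, L = 375 | 0.51 | 11.4 | 1.86 |
| Rising, L = 466 | 0.42 | 9.7 | 2.23 |
| Rising, L = 375 | 0.34 | 8.3 | 2.63 |

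At a 10% full-period risk the crude figure is 4.0% to 6.5%; at 30% it is 12.8% to 19.9%.

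**True doubling of the rate on drug.** The full-period risk would be 1 − 0.8² = 36%. The crude figure is 15.7% to 24.1% if recording stops one month after the last dose. It is 26.6% to 30.5% if off-drug time at the background rate is also counted. The recording window therefore changes the result materially.

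**All risk in the first 3 months.** A 20% risk shows as 18.1% to 19.2%.

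**All-patients column.** With 300 patients at 20% and 30 at 8.3% to 13.1%: (60 + 2.5)/330 = 18.9% to (60 + 3.9)/330 = 19.4%.

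**Zero events.** By the rule of three, 0 events in 30 patients gives an upper 95% bound of 3/30 = 10 per 100 patient-years if a full year each is assumed. At 18.3 patient-years it is 3/18.3 = 16, and at 10.3 it is 3/10.3 = 29.

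**The case against.** The strongest objection is that exposure-adjusted AE tables are routine SAP content, the SAP is not shown, and Section 9.8.2 does not exclude them. Sections 9.4 and 9.6.2.5, however, hand details to the SAP explicitly. Section 9.8.2 does not: it states the summary, and Amendment 04 lists no change to it while revising the statistics sections around it. The SAP could still add the rates, which keeps this a modest point.

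A second objection is that the arm is descriptive only. This is correct, and it means no test is biased. It does not alter the printed percentage, which is all a reader will have for this arm.

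Several limits do stand:

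- Early reactions are barely affected. Section 1.4.1.2.4 places back and neck pain mostly in the first three months, and Section 1.4.1.2.6 places the haemoglobin decrease early in treatment.
- Continued safety visits may add off-drug events and narrow the gap.
- Accrual shape and AE risks are not in the protocol.
- With 30 patients, chance is large: 3 of 30 has an exact 95% interval of about 2% to 27%.
- The remedy has its own bias. If a 20% risk falls entirely in the first three months, a rate per patient-year at risk would make the 1.5 mg arm look about 1.5 to 2.2 times worse than an identical fully exposed arm.

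A reader might go further and infer that the highest dose will look safer across the board, or that the pooled column hides its risk. The documents do not support either. The effect depends on event timing and recording window. The pooled column includes placebo and shifts by about a point. On premature discontinuation the arm will look worse, since Section 4.3 records sponsor-requested withdrawal and Section 3.11.3.1.5 does not count these patients as completers. Nor is a signal in this trial being masked: Section 1.4.1.2.7 reports no cardiovascular event at any dose up to the January 2016 review.

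**Conclusion.** The point holds for events spread over time. As written, Section 9.8.2 puts 1.5 mg percentages based on roughly a third to three-fifths of a year beside arms planned for a full year. A 20% constant-rate risk would appear as about 8% to 13%, and a rate about 1.6 to 2.6 times higher would be needed for the 1.5 mg column to show 20%. These sizes rest on the assumed accrual, a constant hazard, full exposure elsewhere and recording to one month after the last dose. Some shortfall in exposure follows from the dates alone.

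This is a reporting improvement for a descriptive arm. It changes no efficacy conclusion and no formal comparison. Separately, Sections 3.11.3.1.5 and 7.1.2 leave it unclear whether off-drug events enter the tables, and that needs settling whichever summary is used.

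**What to change.** In Section 9.8.2:

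1. Keep the crude counts and percentages.
2. Beside them give, for each arm, patient-years on drug and the number of patients with a first event per 100 patient-years at risk, counted to last dose plus 1 month as in Section 7.1.2. Do this at least for serious, cardiovascular and withdrawal-causing AEs.
3. Add a note that these rates assume a roughly constant hazard and should not be used alone for early-onset reactions.
4. Reconcile Section 3.11.3.1.5 with Section 7.1.2 by stating whether events found at visits after the stop are tabulated. If they are, show them separately from the on-drug window.

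The cost is a few table columns. Section 5.1 already provides for measuring study drug exposure, so no new data are needed. The downside is that rates in a 30-patient arm will be imprecise.
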